6.1.2 Descemetorhexis of the Study Eye

Each patient will undergo descemetorhexis of the investigator-selected study eye at Visit 2 (Day -1). A digital photo of the study eye must be taken immediately before and immediately after descemetorhexis at Visit 2. The investigator will perform descemetorhexis to remove central confluent guttae, removing an area of Descemet membrane with a diameter of [REDACTED]. The longest diameter and the shortest diameter must be recorded in the eCRF. The procedure must be recorded by video to record potential differences in technique among investigators. Also, immediately after the operation, the stripped area will be recorded by photo or video with an adjacent scale to measure the area removed. Detailed guidance for performing the study eye descemetorhexis will be provided in the study manual.

Recommended post-descemetorhexis concomitant therapy is described in Section 5.8.1.

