6.7 Sample Collections

Sample collection, processing, and shipping must be performed according to local laboratory requirements and consistent with detailed procedures described in the study manual.

The volume of blood sampled is planned to be less than 20 mL in a single day and less than 35 mL over the entire study.

7 Statistical and Analytical Plan

A study eye will be identified for each patient. Unless otherwise specified, efficacy will be summarised for the study eye only. Ocular safety summaries by eye will be presented separately for the study eye and the non-study eye. Baseline measurements are the last measurements taken during the screening period (before Visit 2).

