| Difference to Placebo [1]         |                      |                      |                    |
| p-value by Wilcoxon Rank Sum Test | X.XXXX               | X.XXXX               |                    |
| Hodges-Lehmann Estimate           | X.X                  | X.X                  |                    |
| Moses 95% Confidence Interval     | (XX.X, XX.X)         | (XX.X, XX.X)         |                    |
| Central Corneal ECD at Week 1     |                      |                      |                    |
| n                                 | XX                   | XX                   | XX                 |
| Mean (SD)                         | XX.X (XX.XX)         | XX.X (XX.XX)         | XX.X (XX.XX)       |
| Median                            | XX.X                 | XX.X                 | XX.X               |
| Q1, Q3                            | XX.X, XX.X           | XX.X, XX.X           | XX.X, XX.X         |
| Min, Max                          | XX, XX               | XX, XX               | XX, XX             |
| Difference to Placebo [1]         |                      |                      |                    |
| p-value by Wilcoxon Rank Sum Test | X.XXXX               | X.XXXX               |                    |
| Hodges-Lehmann Estimate           | X.X                  | X.X                  |                    |
| Moses 95% Confidence Interval     | (XX.X, XX.X)         | (XX.X, XX.X)         |                    |

...  
 Note: LOCF = last-observation-carried, ECD = Endothelial Cell Density  
 Baseline is defined as the last measurement including unscheduled assessments prior to the administration of first dose of [REDACTED] treatment.  
 Central corneal ECD (both baseline and post-baseline) that are unable to be performed due to corneal oedema are [REDACTED]. Assessment images that are unable to be analysed and categorized as [REDACTED].

[REDACTED] and [REDACTED] by [REDACTED] are [REDACTED]  
[REDACTED]  
[REDACTED]  
[REDACTED]  
[REDACTED] is based on the Wilcoxon rank sum test. The [REDACTED] between [REDACTED] treatment groups and the Moses CIs were estimated with the Hodge-Lehmann method.  
Source Data: Listing 16.2.6.1

<DIRECTORY PATH>PROGRAM NAME Executed: DDMMYYYY hh:mm

Prog Notes: 1. Repeat for scheduled visits.

Table 14.2.1.44

Change from Baseline in Central Corneal Thickness ( $\mu\text{m}$ ) of Study Eye by Visit (LOCF) via Wilcoxon Rank Sum Test  
(Full Analysis Set)

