|   | K-321 QID
(N=XXX) | K-321 BID
(N=XXX) | Placebo
(N=XXX) |
|---|----------------------|----------------------|--------------------|
| Change from Baseline in
Central Corneal Thickness at
Week 1 [1] |                      |                      |                    |
| n   | XX                   | XX                   | XX                 |
| Mean (SD)   | XX.X (XX.XX)         | XX.X (XX.XX)         | XX.X (XX.XX)       |
| Median  | XX.X                 | XX.X                 | XX.X               |
| Q1, Q3  | XX.X, XX.X           | XX.X, XX.X           | XX.X, XX.X         |
| Min, Max  | XX, XX               | XX, XX               | XX, XX             |
| Difference to Placebo [2]   |                      |                      |                    |
| p-value by Wilcoxon Rank
Sum Test                                  | X.XXXX               | X.XXXX               |                    |
| Hodges-Lehmann Estimate   | X.X                  | X.X                  |                    |
| Moses 95% Confidence
Interval                                      | (XX.X, XX.X)         | (XX.X, XX.X)         |                    |

Note: Baseline is defined as the last measurement including unscheduled assessments prior to administration of first dose of study eye drops. The values for the change from baseline in central corneal thickness and the values for the change from baseline in corneal topography are [REDACTED].

Change from baseline is defined as the post baseline value minus the baseline value for the given assessment. For the change from baseline, only patients with a value at both baseline visit and the specific post-baseline visit are included.

[2] P-value is based on the Wilcoxon rank sum test. The median differences between the treatment groups and the Moses CIs were estimated with the Hodge-Lehmann method.

Source Data: Listing 16.2.6.3

<DIRECTORY PATH>PROGRAM NAME Executed: DDMMYYYY hh:mm

Prog Notes: Repeat for scheduled visits.

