Note: BCVA = Best Corrected Visual Acuity, ETDRS= Early Treatment Diabetic Retinopathy Study

ECD = Endothelial Cell Density

Ass [REDACTED] be analysed and categorized as [REDACTED]

[figure not shown]
or [REDACTED] are not included.

Only [REDACTED] a observed are included.

Assessments after rescue keratoplasty are included using the collected values.

<DIRECTORY PATH>PROGRAM NAME Executed: DDMMYYYY hh:mm

Figure 14.2.1.42  
Time to Achieve Intervention of Rescue Therapy (Kaplan-Meier Plot)  
(Full Analysis Set)

Note: Time to Achieve Intervention of Rescue Therapy = Date of Achieving Intervention of Rescue Therapy - Day 1 + 1.

Patient is considered having received rescue therapy if the patient 1) received rescue surgical procedure (penetrating keratoplasty or endothelial keratoplasty) during the study. 2) withdrawal with potential for surgical procedure. 3) withdrawal with potential for Rho kinase Inhibitor treatment.]

Patient's study discontinuation date is used as the rescue therapy date if the patient withdrawal with potential for surgical procedure or Rho kinase Inhibitor treatment.

Patients who complete follow-up or discontinue the study without achieving the specified endpoint are

Source Data: T14.2.1.42

DIRECTORY PATH>PROGRAM NAME Executed: DDMMYYYY hh:mm

[figure not shown]
Programming note: Please show x-axis as Day 1 to Day 371. Please display y-axis label as 'Probability of Achieving Intervention of Rescue Keratoplasty (%)'.

Please display all treatment groups: K-321 QID, K-321 BID, Placebo

Figure 14.2.1.43

Central Corneal ECD (cells/mm^2) of Study Eye performed by Specular Microscopy (LOCF) (Time Series Plot) (Full Analysis Set)

Note: LOCF = last-observation-carried forward, ECD = Endothelial Cell Density  
Baseline is defined as the last measurement including unscheduled assessments prior to the administration of first dose of treatment.  
Central corneal ECD (both baseline and post-baseline) that are unable to be performed due to

assessment and analysis and central corneal ECD by [redacted] are [redacted].

[redacted]

T14 43

DIRECTORY PATH>PROGRAM NAME Executed: DDMMYYYY hh:mm

Programming note: Please show x-axis according to the analysis visit. Please display y-axis label as 'Mean(+/-SD) Central Corneal ECD (cells/mm^2) by Specular Microscopy'.  
Please display all treatment groups: K-321 QID, K-321 BID, Placebo  
Below the figure please include the N counts at each visit.  

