Please include N counts for each treatment arm at the annotation.

Figure 14.2.1.44

Change from Baseline in Central Corneal Thickness ( $\mu\text{m}$ ) of Study Eye (LOCF) (Time Series Plot)  
(Full Analysis Set)

Repeat Figure 14.2.1.43 for Change from Baseline in Central Corneal Thickness

Note: Baseline is defined as the last [REDACTED] measurement including unscheduled assessments prior to  
inistration of first dose of st [REDACTED] n  
[REDACTED] central corneal [REDACTED]  
[REDACTED] atoplasty are [REDACTED]

[REDACTED] m baseline is defined as the post baseline value minus the baseline value for the given  
assessment. For the change from baseline, only patients with a value at both baseline visit and the  
specific post-baseline visit are included.

Source Data: T14.2.1.44

[figure not shown]
DIRECTORY PATH>PROGRAM NAME Executed: DDMMYYYY hh:mm

Programming note: Please show x-axis according to the analysis visit. Please display y-axis label as  
'Mean(+/-SD) Change from Baseline in Central Corneal Thickness ( $\mu\text{m}$ )'.

Please display all treatment groups: K-321 QID, K-321 BID, Placebo

Figure 14.2.1.45

Proportion of Patients Who Achieve No Corneal Oedema of Study Eye (LOCF) (Bar Chart)  
(Full Analysis Set)

Note: No corneal oedema is defined as absent of oedema in all three layers of cornea, including epithelial, stromal, and endothelial.

corneal oedema assessments are [REDACTED]. Patients who received a rescue keratoplasty are [REDACTED].

Numbers presented on the bars are the number of patients who achieve no corneal oedema of study eye for each visit under each treatment arm.

Source Data: T14.2.1.45

DIRECTORY PATH>PROGRAM NAME Executed: DDMMYYYY hh:mm

Programming note: Please show x-axis according to the analysis visit. Please display y-axis label as 'Proportion of Patients Who Achieve No Corneal Oedema'.

Please display all treatment groups on the same page: K-321 QID, K-321 BID, Placebo

Please include the n counts above each bar for each treatment arm and each visit for subjects who achieved the endpoint.

Figure 14.2.1.46  
Change from Baseline in BCVA by ETDRS of Study Eye (LOCF) via Wilcoxon Rank Sum Test (Time Series Plot)  
(Full Analysis Set)

[figure not shown]
Repeat Figure 14.2.1.43 for Change from Baseline in BCVA

Note: BCVA = Best Corrected Visual Acuity; ETDRS = Early Treatment Diabetic Retinopathy Study  
Baseline is defined as the last measurement including unscheduled assessments prior to the  

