administration of first dose. [redacted]  
[redacted] surgery are  
[redacted] ven  
assessment. For the change from baseline, only patients with a value at both baseline visit and the  
specific post-baseline visit are included.  
Source Data: T14.2.1.46

DIRECTORY PATH>PROGRAM NAME Executed: DDMMYYYY hh:mm

Programming note: Please show x-axis according to the analysis visit. Please display y-axis label as  
'Mean(+/-SD) Change from Baseline in BCVA by ETDRS Letter Score'.  
Please display all treatment groups: K-321 QID, K-321 BID, Placebo

Figure 14.2.1.47  
BCVA by ETDRS by Central ECD Gradeability by Visit (Box Plot)  
(Full Analysis Set)

Note: BCVA = Best Corrected Visual Acuity, ETDRS= Early Treatment Diabetic Retinopathy Study  
ECD = Endothelial Cell Density  
Baseline is defined as the last [REDACTED] measurement including unscheduled assessments prior to the  
[REDACTED] tion of first dose of [REDACTED]  
[REDACTED] Central corneal ECD include [REDACTED] Central corneal ECD assessments or the Central corneal  
[REDACTED] ments that could not be performed [REDACTED] o oedema.  
Source Data: Table 14.2.1.47

[figure not shown]
DIRECTORY PATH>PROGRAM NAME Executed: DDMMYYYY hh:mm

Programming note: Please show x-axis according to the subgroups [REDACTED] and [REDACTED]. Please  
display y-axis label as 'BCVA by ETDRS Letter Score'.

Please display 'All Post-Baseline Visits' in the first page, then start the second page with  
'Baseline', 'Week X'... Each visit should be on a separate page.

In each page please display all treatment groups and Total: Total, K-321 QID, K-321 BID, Placebo  
In each page please include number of subjects under each treatment arm and subgroups under the plot.

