**Figure 14.2.1.48**  
BCVA by ETDRS by Central ECD Value by Visit (Scatter Plot)  
(Full Analysis Set)

Note: BCVA = Best Corrected Visual Acuity, ETDRS= Early Treatment Diabetic Retinopathy Study  
ECD = Endothelial Cell Density  
Baseline is defined as the last [redacted] measurement including unscheduled assessments prior to the administration of first dose of [redacted] ment.

[figure not shown]
Source Data: Table 14.2.1.48

DIRECTORY PATH>PROGRAM NAME Executed: DDMMYYYY hh:mm

Programming note: Please show x-axis according to the subgroups '1 < Central ECD Value <= Mean', 'Central ECD Value > Mean' 'and [REDACTED]'. Please display y-axis label as 'BCVA by ETDRS Letter Score'. Please display 'All Post-Baseline Visits' in the first page, then start the second page with 'Baseline', 'Week X'... Each visit should be on a separate page.

In each page please display all treatment groups: Total, K-321 QID, K-321 BID, Placebo  
In each page please include number of subjects under each treatment arm and subgroups under the plot.  
Please display the spearman correlation and p-value under the figure for each treatment group and total.

Figure 14.2.1.49  
Correlation between BCVA by ETDRS and Central Corneal ECD (Include [REDACTED] (Pearson and Spearman)  
(Full Analysis Set)

Note: BCVA = Best Corrected Visual Acuity, ETDRS= Early Treatment Diabetic Retinopathy Study  
ECD = Endothelial Cell Density  
Central corneal ECD assessments that are unable to be performed due [REDACTED].  
Ass [REDACTED] be a [REDACTED] ed an [REDACTED] s [REDACTED].  
or [REDACTED] by [REDACTED] [REDACTED] [REDACTED] [REDACTED].  
Ass [REDACTED] are [REDACTED] [REDACTED] [REDACTED].  
Source Data: Table 14.2.1.49

<DIRECTORY PATH>PROGRAM NAME Executed: DDMMYYYY hh:mm

Programming note: Please display x-axis label as 'Central Corneal ECD (cells/mm^2)'. Please display y-axis label as 'BCVA by ETDRS Letter Score'.  
Please display the scatter lot for total and each treatment group in separate pages.

Please include the spearman and perason correlation values and the corresponding p-values under the figure for each treatment group and total.

Figure 14.2.1.50

Correlation between BCVA by ETDRS and Central Corneal ECD (Include [REDACTED] Data) (No Corneal Oedema)  
(Pearson and Spearman)  
(Full Analysis Set)

Repeat Figure 14.2.1.49 but only include the visits where there is No Corneal Oedema.

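### The addendum shells set baseline before first dose, the protocol before Visit 2; an unscheduled reading between surgery and first dose would become baseline under the shells

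*SAP*

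**What the plan says.** The opening of Protocol section 7 states: "Baseline measurements are the last measurements taken during the screening period (before Visit 2"). The SAP addendum, in Appendix 1, uses a different cut-off in its table and figure notes:

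- Table 14.2.1.43 (cell density): "Baseline is defined as the last measurement including unscheduled assessments prior to the administration of first dose of", with the next word blacked out.
- Figure 14.2.1.43: "Baseline is defined as the last measurement including unscheduled assessments prior to the administration of first dose of treatment".
- Table 14.2.1.44 (corneal thickness): "Baseline is defined as the last measurement including unscheduled assessments prior to administration of first dose of study eye drops".
- Figure 14.2.1.46 (BCVA): "Baseline is defined as the last measurement including unscheduled assessments prior to the", continuing to the first dose.

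Tables 14.2.1.46, .47 and .48 and Figures 14.2.1.44, .47 and .48 carry the same rule, but with a word blacked out after the word last. Figure 14.2.1.48, for example, has "Baseline is defined as the last [redacted] measurement including unscheduled assessments prior to the administration of first dose of".

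On timing, Protocol section 6.1.2 says "Each patient will undergo descemetorhexis of the investigator-selected study eye at Visit 2", which is Day -1. Sections 3.1 and 5.2 put the first dose at Visit 3 (Day 1), once that visit's measurements are done.

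**The concern.** The two definitions differ by the interval from Visit 2 to first dose, and the operation falls inside it. The shells expressly admit unscheduled readings. A thickness, acuity or cell density reading taken after surgery but before the first drop would therefore be baseline under the shell rule and not under the protocol.

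The notes define change as the later value minus baseline. For an affected patient, the thickness or acuity change would be measured from a freshly operated eye instead of the diseased eye that entered the trial. That is a different quantity from the one in Protocol section 7.2, reported under the same name. No legible text in the addendum gives a reason for the change of cut-off.

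**Working it through.** **Timeline from the documents**

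| Step | When | Source | Thickness, BCVA or ECD scheduled? |
|---|---|---|---|
| Screening | Visit 1 | Protocol Table 6-1 | Yes |
| Protocol cut-off | Before Visit 2 | Protocol section 7 | n/a |
| Descemetorhexis, randomisation | Visit 2, Day -1 | Sections 5.1, 6.1.2 | No |
| Visit 3 measurements | Day 1, before dosing | Sections 3.1, 5.2; Table 6-1 | No |
| First dose (shell cut-off) | Day 1 | Sections 3.1, 5.2 | n/a |
| Next scheduled readings | Week 1 | Table 6-1 | Yes |

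**Which value each rule selects**

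1. Scheduled readings only: both rules pick the Visit 1 value and agree.
2. Unscheduled reading on the day of Visit 2 but before surgery: the rules pick different values, both pre-operative, so this is harmless.
3. Unscheduled reading after surgery and before first dose: the protocol keeps the screening value and the shells take the post-operative one.

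Only case 3 matters. The documents do not say whether it occurred.

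**Where baseline enters.** The .44 and .46 tables and figures subtract it. In .43, .47 and .48 only a baseline row is visibly affected. The primary endpoint (Protocol section 7.1) is a Week 12 level and subtracts nothing.

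**Illustration on assumed inputs.** The thickness values, SD, swelling, true difference and frequencies below are not in the documents.

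- One patient: screening 600 µm, post-operative 700 µm, Week 12 650 µm. Protocol rule: 650 − 600 = +50 µm. Shell rule: 650 − 700 = −50 µm.
- One arm of n = 20 with k affected patients and swelling s: the mean change moves by −k·s/20. For k = 1 and s = 50, 100, 150 µm this is −2.5, −5.0, −7.5 µm.
- For scale, with an SD of change of 40 µm, the standard error of a difference in two means is 40·√(1/20 + 1/20) = 12.6 µm. In simulation the Hodges-Lehmann difference has an SD of about 13 µm, and one affected patient shifts it by about 2.3, 3.4 or 3.7 µm for the three values of s.
- Chance imbalance: let each compared arm have a Binomial(20, p) number affected, with probabilities f(k). P(counts differ) = 1 − Σ f(k)². For p = 1%, 2%, 5% this is 30%, 48%, 69%; the chance of differing by two or more is 3%, 8%, 25%. Expected affected patients among 60: 0.6, 1.2, 3.
- Wilcoxon test at two-sided 0.05, 20,000 simulated trials per setting. With no true difference, rejection is 0.046 to 0.050 and the mean Hodges-Lehmann difference stays within 0.5 µm of zero. With an assumed true difference of 38 µm, power is 81% at p = 0 and 78%, 74%, 72% at p = 5% for s = 50, 100, 150 µm.

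**The case against.** The strongest reply is that this is one repeated footnote, unevenly redacted. Table 14.2.1.44 shows no mark after the word last, while Figure 14.2.1.44 does. Table 14.2.1.46 shows one and Figure 14.2.1.46 does not. A hidden word, possibly a qualifier, may therefore sit in every shell, and the clean-looking notes cannot rule that out. This stands and limits confidence.

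Second, the change-score notes require a value at a baseline visit as well as at the later visit. For thickness and BCVA, the only scheduled visit before first dose with a reading is Visit 1. That points towards a visit-based baseline. It does not settle the matter, because the same notes admit unscheduled readings.

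Third, Protocol section 7.7 leaves data conventions to the SAP, and the addendum's introduction says it does not repeat what primary SAP v2.0 defined. A governing definition may be there, and v2.0 is not among the documents. This also stands: shell notes are weak evidence of how baseline was actually derived.

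Fourth, the trigger is narrow (Day -1 to Day 1), nothing suggests such a reading was taken, and every magnitude above rests on assumptions. All true.

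What remains is that the legible wording contradicts the protocol, and that following it would give the wrong subtrahend in case 3.

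**Conclusion.** A minor inconsistency that holds conditionally, with medium confidence. The legible shell notes and Protocol section 7 define baseline differently, and surgery lies between the two cut-offs. The result changes only for patients with an unscheduled reading after surgery and before first dose; that number is unknown and may be zero.

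A reader might infer more than this. The documents do not support any of the following:

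- **That baseline becomes post-operative for patients generally.** Table 6-1 schedules none of the three measures at Visit 2 or 3, so scheduled data give the same baseline under both rules.
- **That the treatment comparison is biased.** The readings precede dosing in a randomised, masked trial, so any shift is equally likely in each arm. The cost is added noise and possible chance imbalance with about 20 patients per arm.
- **That the main result is at risk.** The addendum covers additional analyses defined after the Week 12 unmasking, and the primary endpoint is an absolute cell density.
- **That Table 14.2.1.45 has the same fault.** It has a baseline row for oedema but no legible baseline definition.

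The power and imbalance figures show scale on assumed inputs and are not estimates for this trial.

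**What to change.** In the five sets of shells (.43, .44, .46, .47 and .48), replace the first-dose cut-off with the protocol's, for example: *Baseline: the most recent screening-period value, scheduled or unscheduled, obtained before Visit 2.* List any reading taken between surgery and first dose, but do not use it as baseline. Report how many patients' baseline would differ under the first-dose rule; if none, one sentence closes the point. State the baseline used in Table 14.2.1.45 as well.

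Confirm that primary SAP v2.0 uses the same cut-off. This matters beyond the addendum, because the secondary endpoints in Protocol section 7.2 on thickness change, return to baseline thickness and corneal clearance all depend on baseline.

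The cost is one phrase, one derivation rule and one count, with no new data. If SAP v2.0 has the first-dose cut-off, the same phrase must change there.

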**Table 14.2.1.45**  
Proportion of Patients Who Achieve No Corneal Oedema of Study Eye by Visit (LOCF)  
(Full Analysis Set)

|   | K-321 QID
(N=XXX) | K-321 BID
(N=XXX) | Placebo
(N=XXX) |
|---|----------------------|----------------------|--------------------|
| Patients Achieved No Corneal Oedema at Baseline |                      |                      |                    |
| Achieved n(%)                                   | XX (XX.X)            | XX (XX.X)            | XX (XX.X)          |
| Not Achieved n(%)                               | XX (XX.X)            | XX (XX.X)            | XX (XX.X)          |
| Difference to Placebo [1]                       |                      |                      |                    |
| Response Rate Difference (%)                    | XX.X                 | XX.X                 |                    |
| 95% Confidence Interval                         | (XX.X, XX.X)         | (XX.X, XX.X)         |                    |
| p-value   | X.XXXX               | X.XXXX               |                    |
| ...   |                      |                      |                    |

Note: No corneal oedema is defined as absent of oedema in all three layers of cornea, including epithelial, stromal, and endothelial.

corneal oedema of study are .  
The p-value is based on the Pearson Chi-square test </the Fisher's exact test with unconditional confidence interval>.

Source Data: Listing 16.2.6.6

<DIRECTORY PATH>PROGRAM NAME Executed: DDMMMYYYY hh:mm

Prog Notes: Repeat for scheduled visits.

